### **5.10 Other Efficacy Outcome Variable**

All biopsies will be collected and analysed post unblinding of the study. Data will be analysed descriptively.

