6.1 Primary Objective

The objective of this trial is:

To map the molecular mechanisms of action responsible for the *in-vivo* protection of Aspirin-induced enteropathy by Bif195 in humans.

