6.7 Endpoints

Endpoints, all exploratory:

- The effects of daily intake of Bif195 versus placebo on transcriptomics measured in ventricle and upper small intestinal mucosal biopsies obtained before and after a 4-week ASA challenge
- The effects of daily intake of Bif195 versus placebo on microbiota composition profile measured in ventricle and upper small intestinal mucosal biopsies obtained before and after a 4-week ASA challenge
- The effects of daily intake of Bif195 versus placebo on proteomics profile measured in ventricle and upper small intestinal mucosal biopsies obtained before and after a 4-week ASA challenge
- The effects of daily intake of Bif195 versus placebo on metabolomics profile measured in small intestinal luminal fluid samples obtained before and after a 4-week ASA challenge
- The effects of Bif195 versus placebo administration on the Lanza score of the ventricle obtained before and after a 4-week ASA challenge
- The effects of Bif195 versus placebo administration on the Lanza score of the duodenum obtained before and after a 4-week ASA challenge

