6.9.8 Statistics and power calculation

Data will be entered into a database and analysed using statistical software. The effect of the intervention on the endpoints will be assessed using paired statistical analysis and the level of significance will be set to 0.05. Pathway analysis will also be performed using a more explorative approach.

Previous studies using the same endoscopy procedure with biopsies being analysed for arrays of gene expression have showed an approximate negative binomial distribution and a coefficient of variation of 0.344. Assuming a negative binomial distribution of the data in the present study, we have calculated that a sample size of 20 will result in a power of 0.95 for identifying genes that are down or up-regulated more than 1.5-fold as a consequence of Bif195 intervention at a significance level of 0.05. In order to achieve this statistical power, we aim to have 20 subjects completing the intervention. Assuming a drop-out rate of around 20%, we aim to randomise 25 subjects.

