### 1.2 Summary

The table below provide an overview of all analyses performed on the primary, secondary and exploratory endpoints.

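### The protocol promises paired tests at 0.05 and sizes the trial on gene expression, but the SAP only describes the biopsy data, so no SAP test carries the stated 0.95 power

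*SAP*

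**What the plan says.** Protocol 6.1 gives one objective: "To map the molecular mechanisms of action responsible for the" protection seen with Bif195. Protocol 6.7 lists six endpoints under the label "Endpoints, all exploratory". Four are omics: transcriptomics, microbiota and proteomics in mucosal biopsies, and an endpoint "on metabolomics profile measured in small intestinal luminal fluid samples obtained before and after a 4-week ASA challenge". The other two are Lanza scores.

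Protocol 6.9.8 says that the effect on the endpoints "will be assessed using paired statistical analysis and the level of significance will be set to 0.05". It exempts no endpoint; pathway analysis is an addition. It then states that "a sample size of 20 will result in a power of 0.95 for identifying genes that are down or up-regulated more than 1.5-fold", and continues: "In order to achieve this statistical power, we aim to have 20 subjects completing the intervention". This is the only justification of the sample size in either document.

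SAP 1.2 presents its table as an "overview of all analyses performed on the primary, secondary and exploratory endpoints". The table holds the Lanza score (GEE) and the blood safety and efficacy parameters (mixed model), and nothing else. The one SAP statement about the biopsies is in 5.10: "All biopsies will be collected and analysed post unblinding of the study. Data will be analysed descriptively". The supplied SAP text names no omics platform, no gene-level model and no luminal fluid.

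**The concern.** A paired test at 0.05 and description only cannot both be the plan for the same data. The conflict falls on the measurements that serve the protocol's single objective and that set its sample size.

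Power is a property of a test with a rejection rule, and a descriptive analysis has none. The tests that the SAP does plan are on an ordinal score and on blood values, to which a gene-expression coefficient of variation and a 1.5-fold change do not apply. A later reader could not tell whether gene-level p-values were planned or were added afterwards. Because SAP 5.10 puts the biopsy analysis after unblinding, any contrast, model or error-control rule still open would be chosen when allocation can be known.

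**Working it through.** **1. Reproduce the protocol's figure.** Inputs from protocol 6.9.8: coefficient of variation 0.344, fold change 1.5, n = 20, alpha 0.05. Two-sided testing is taken from SAP 5.1. Assumptions: 0.344 is the SD on the natural-log scale; the mean count is large, so its 1/mean variance term is ignored; within-subject correlation is zero. The documents give neither mean count nor correlation.

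- Effect: ln(1.5) = 0.405
- Variance of a difference between two samples: 2 × 0.344² = 0.2367
- Standard error: sqrt(0.2367 / 20) = 0.1088
- Noncentrality: 0.405 / 0.1088 = 3.73

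| Calculation | Power |
|---|---|
| Normal approximation | 0.961 |
| Unpaired t, 38 df | 0.953 |
| Paired t, 19 df, correlation 0 | 0.942 |

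The stated 0.95 lies in this range. A mean count of about 122 in the normal approximation gives 0.950. A one-sided 0.05 test gives 0.981 and does not match. The number randomised also follows: 20 / (1 − 0.20) = 25. So 0.95 is the power for one gene at an unadjusted two-sided 0.05.

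**2. Look for the SAP test that it belongs to.**

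| Protocol 6.7 endpoint | Protocol 6.9.8 | SAP |
|---|---|---|
| Transcriptomics, biopsies | paired, 0.05; basis of n | descriptive (5.10), not named |
| Microbiota, biopsies | paired, 0.05 | descriptive (5.10), not named |
| Proteomics, biopsies | paired, 0.05 | descriptive (5.10), not named |
| Metabolomics, luminal fluid | paired, 0.05 | not named |
| Lanza, ventricle and duodenum | paired, 0.05 | GEE (5.4), two-sided 5% (5.1) |

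Four of six endpoints have no SAP test, and the number of SAP tests to which the 0.95 applies is zero. The Lanza score is not affected.

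**3. What adding a test would do to the 0.95.** The same inputs, paired t with 19 df and zero correlation:

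| Test | Power per gene |
|---|---|
| After-values, alpha 0.05 | 0.942 |
| After-values, alpha 0.01 | 0.79 |
| After-values, alpha 0.001 | 0.47 |
| Difference in change from baseline, alpha 0.05 | 0.71 |

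The last row uses four samples per subject: variance 4 × 0.344² = 0.4733, standard error sqrt(0.4733 / 20) = 0.1538, noncentrality 0.405 / 0.1538 = 2.64. The smaller alphas only illustrate a stricter threshold, since a false-discovery-rate cutoff depends on the data. Positive within-subject correlation would raise every row.

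**The case against.** The strongest reply is that all six endpoints are exploratory and the omics work is staged: protocol 8.2 leaves the laboratory contracts until after the study has been conducted, and SAP 5.10 puts the biopsy analysis after unblinding. On this view the SAP was written for the clinical and blood data, and description is proper for the rest. Part of this stands. Description would be acceptable, and no confirmatory claim is at risk. But the protocol applies the exploratory label and still promises paired tests and a powered sample size, the SAP says that its table covers exploratory endpoints, and neither document refers to a separate omics plan.

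A reader might infer four stronger things that the documents do not support.

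- *The power is miscalculated.* It reproduces.
- *The SAP cancels the protocol's tests.* The SAP does not say so, and protocol 6.9.8 is current text. The documents disagree, and the SAP has no test that matches the power statement; that is as far as the point goes.
- *Luminal-fluid metabolomics has been dropped.* The supplied SAP text does not name it, but protocol 6.2 itself uses biopsies loosely to include metabolomics, and SAP 5.10 may do the same. This is a secondary ambiguity.
- *The plan will generate many false-positive genes.* The SAP plans no gene-by-gene tests, so this is no consequence of it. Nor does the absence of multiplicity adjustment in SAP 5.11 settle the matter for omics, because its heading covers primary and secondary efficacy only.

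**Conclusion.** The point holds as a contradiction between protocol 6.9.8 and SAP 5.10, together with a SAP 1.2 table that omits the omics endpoints it is said to cover. Its size is four of six endpoints without a planned between-treatment test and a sample-size rationale attached to no SAP test. It should be fixed, but it is neither an arithmetic error nor a threat to a confirmatory conclusion.

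The contradiction rests on the text alone. The reproduction of 0.95 (0.94 to 0.96) rests on reading 0.344 as a log-scale SD with large counts and no gain from pairing. The statement about omission is limited to the supplied SAP text, from which figures and some pages are absent.

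**What to change.** Choose one option and make both documents agree.

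**Option A, test.** Before unblinding, replace the descriptive statement in SAP 5.10 with a paired Bif195-versus-placebo analysis for each omics endpoint in protocol 6.7, luminal-fluid metabolomics included. Use terms for subject, treatment and period, and name one contrast, preferably after-values adjusted for that period's baseline. State an error-control rule, for example Benjamini-Hochberg within each tissue and platform; the rule and its level are the sponsor's choice, since neither document sets them. Add the rows to the SAP 1.2 table. In protocol 6.9.8, state that 0.95 is per gene at an unadjusted 0.05 and that power under the chosen contrast and rule may be lower, as step 3 of the working illustrates. Without that sentence the 0.95 would still match no SAP test.

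**Option B, describe.** Amend protocol 6.9.8 to withdraw the promised tests for the four omics endpoints and to state that the power calculation supports no planned test. List all four, with luminal-fluid metabolomics named, as descriptive in SAP 5.10 and the SAP 1.2 table.

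**Cost.** Option A needs SAP text and some analysis work, and brings fewer genes declared and possibly a per-gene power below 0.95. Option B needs only text. Neither needs new subjects, visits or samples.

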### **5.11 Control of Multiplicity for the Primary and secondary Efficacy Analysis**

No adjustment for multiplicity is done.

### **5.12 Subject Disposition, Demographics and Other Characteristics**

Subject disposition demographics and other characteristics will be reported descriptively.

## **6 Software**

All statistical analyses will be computed using the statistical software SAS®, Release 9.3 or later versions.

